APPENDIX D: FIGURE LAYOUTS

Protocol: GLS27-005

Figure 14.2.2.1

Line Plot of Mean (+/- SD) PEEP Results During Intubation by Study Day (ITT Population)

Figure 14.2.2.2 Line Plot of Mean (+/- SD) PEEP Results During Intubation by Study Day (PP Population)

Figure 14.3.4.1

Line Plots of Mean (+/-SD) Vital Sign Results by Test and Study Day (Safety Population)

Figure 14.3.4.2

Line Plots of Mean (+/-SD) 12-Lead ECG Results by Test and Study Day (Safety Population)

APPENDIX E: LISTING LAYOUTS

Listing 16.2.1 Subject Disposition

Treatment: GLS-1027 120 mg

Subject	Informed	Randomizati	onITT	mITT	Safety	PP	First Dose	Study	Study Completion
ID	Consent Date	Date	Population [1]	Population [2]	Population [3]	Population [4]	Date/Time	Completion Status	or Discontinuation Date (Study Day)
xxxx	yyyy-mm-dd	yyyy-mm-dd	Yes/No	Yes/No	Yes/No	Yes/No	yyyy-mm-dd hh:mm	xxxxxxxxx	yyyy-mm-dd (xx)
xxxxx	yyyy-mm-dd	yyyy-mm-dd	Yes/No	Yes/No	Yes/No	Yes/No	yyyy-mm-dd hh:mm	xxxxxxxxx	yyyy-mm-dd (xx)
xxxxx	yyyy-mm-dd	yyyy-mm-dd	Yes/No	Yes/No	Yes/No	Yes/No	yyyy-mm-dd hh:mm	xxxxxxxxx	yyyy-mm-dd (xx)
xxxxx	yyyy-mm-dd	yyyy-mm-dd	Yes/No	Yes/No	Yes/No	Yes/No	yyyy-mm-dd hh:mm	xxxxxxxxx	yyyy-mm-dd (xx)
xxxx	yyyy-mm-dd	yyyy-mm-dd	Yes/No	Yes/No	Yes/No	Yes/No	yyyy-mm-dd hh:mm	xxxxxxxxx	yyyy-mm-dd (xx)
xxxx	yyyy-mm-dd	yyyy-mm-dd	Yes/No	Yes/No	Yes/No	Yes/No	yyyy-mm-dd hh:mm	xxxxxxxxx	yyyy-mm-dd (xx)
xxxx	yyyy-mm-dd	yyyy-mm-dd	Yes/No	Yes/No	Yes/No	Yes/No	yyyy-mm-dd hh:mm	xxxxxxxxx	yyyy-mm-dd (xx)
xxxxx	yyyy-mm-dd	yyyy-mm-dd	Yes/No	Yes/No	Yes/No	Yes/No	yyyy-mm-dd hh:mm	xxxxxxxxx	yyyy-mm-dd (xx)

^[1] The Intent-to-treat (ITT) Population includes all randomized to treatment allocation.

Programming Note: Repeat for each treatment group.

^[2] The modified intention to treatment (mITT) population includes all participants who are randomized to a treatment allocation, and who have received at least one dose of study drug.

^[3] The Safety Population includes all subjects who received at least one dose of study drug.

^[4] The PP Population includes all safety subjects who complete the trial by meeting the endpoint or being discharged within 14 days without meeting the endpoint.

Protocol: GLS27-005

Listing 16.2.2 Protocol Deviations

Treatment: GLS-1027 120 mg

Deviation Date (Study Day)	Deviation Category	Description
yyyy-mm-dd (xx)	Major/Minor	XXXXXX
	yyyy-mm-dd (xx)	yyyy-mm-dd (xx) yyyy-mm-dd (xx) Major/Minor

Programming Note: Repeat for each treatment group.

Listing 16.2.3 Inclusion/Exclusion Criteria

Treatment: GLS-1027 120 mg

Subject ID	All eligibility criteria met	Criterion not met	Criterion Description	
xxxxx	Yes/No	Inclusion xx/Exclusion xx	xxxxxxx	
XXXXX	Yes/No	Inclusion xx/Exclusion xx	xxxxxxx	
xxxxx	Yes/No	Inclusion xx/Exclusion xx	xxxxxxx	
XXXXX	Yes/No	Inclusion xx/Exclusion xx	xxxxxxx	
xxxxx	Yes/No	Inclusion xx/Exclusion xx	xxxxxxx	
xxxxx	Yes/No	Inclusion xx/Exclusion xx	xxxxxxx	
xxxxx	Yes/No	Inclusion xx/Exclusion xx	xxxxxxx	
XXXXX	Yes/No	Inclusion xx/Exclusion xx	XXXXXXX	

Programming Note: Repeat for each treatment group. If more than one criterion IDs are selected for a subject, list each one on a separate line.

Listing 16.2.4.1
Demographic and Baseline Characteristics

Treatment: GLS-1027 120 mg

Subject ID	Age (years)	Gender at Birth/ Current Gender	Taking Approved Form of Birth Control	Race	Ethnicity	Height (cm)	Weight (kg)	BMI (kg/m^2)
xxxxxx	XX	Male/Female	Yes	xxxxxxxxxxx	xxxxxxxxxxx	xx.x	xx.x	xx.x
xxxxx	XX	Male/Female	No: Reason	xxxxxxxxxxx	XXXXXXXXXXX	xx.x	xx.x	xx.x
xxxxx	xx	Male/Female	N/A	xxxxxxxxxxx	XXXXXXXXXXX	xx.x	xx.x	xx.x
xxxxx	xx	Male/Female	Yes/No	xxxxxxxxxxx	XXXXXXXXXXX	xx.x	xx.x	xx.x
xxxxx	xx	Male/Female	Yes/No	xxxxxxxxxxx	xxxxxxxxxxx	xx.x	xx.x	xx.x
xxxxx	xx	Male/Female	Yes/No	xxxxxxxxxxx	xxxxxxxxxxx	xx.x	xx.x	xx.x
xxxxx	xx	Male/Female	Yes/No	xxxxxxxxxxx	xxxxxxxxxxx	xx.x	xx.x	xx.x
xxxxx	xx	Male/Female	Yes/No	xxxxxxxxxxx	xxxxxxxxxxx	xx.x	xx.x	xx.x

Baseline is the last non-missing value prior to first dose of study treatment.

date time

Programming Note: Repeat for each treatment group.

Page 1 of x

GeneOne Life Science Inc. Protocol: GLS27-005

Listing 16.2.4.2 Medical History

Treatment: GLS-1027 120 mg

Subject ID	Any medical history	System Organ Class/ Preferred Term/ Verbatim Term	Start Date	Ongoing	Stop Date
xxxxx	Yes/No	xxxxxxxxx/ xxxxxxxxx/	yyyy-mm-dd	Yes/No	yyyy-mm-dd
		xxxxxxxxx xxxxxxxxx/ xxxxxxxxx/ xxxxxxxx	yyyy-mm-dd	Yes/No	yyyy-mm-dd
xxxxx	Yes/No	xxxxxxxxx/ xxxxxxxxx/	yyyy-mm-dd	Yes/No	yyyy-mm-dd
		xxxxxxxxx xxxxxxxxx/ xxxxxxxxx/ xxxxxxxx	yyyy-mm-dd	Yes/No	yyyy-mm-dd
xxxxx	Yes/No	xxxxxxxxx/ xxxxxxxxx/ xxxxxxxxx	yyyy-mm-dd	Yes/No	yyyy-mm-dd
		xxxxxxxxx/ xxxxxxxxx/ xxxxxxxxx	yyyy-mm-dd	Yes/No	yyyy-mm-dd

MedDRA = Medical Dictionary for Regulatory Activities.
Medical history terms are coded using MedDRA version 23.0.

Programming Note: Repeat for each treatment group.

Listing 16.2.4.3
Prior and Concomitant Medications

Treatment: GLS-1027 120 mg

Subject ID	ATC Class/ Preferred Name/ Verbatim Term	Start Date (Study Day)	End Date (Study Day)	Dose	Units	Route	Frequency	Indication
xxxxxx	xxxxxxxxx/ xxxxxxxxx/ xxxxxxxxx	yyyy-mm-dd (xx)	yyyy-mm-dd (xx)	xxxxxxxxx	xxxxxxxxx	xxxxxxxxx	xxxxxxxxx	xxxxxxxxx
	xxxxxxxxx/ xxxxxxxxx/ xxxxxxxx	yyyy-mm-dd (xx)	yyyy-mm-dd (xx)	xxxxxxxxx	xxxxxxxxx	xxxxxxxx	xxxxxxxxx	xxxxxxxxx
xxxxx	xxxxxxxxx/ xxxxxxxxx/ xxxxxxxxx*	yyyy-mm-dd (xx)	yyyy-mm-dd (xx)	xxxxxxxxx	xxxxxxxxx	xxxxxxxx	xxxxxxxxx	xxxxxxxxx
	xxxxxxxxx/ xxxxxxxxx/ xxxxxxxx*	yyyy-mm-dd (xx)	yyyy-mm-dd (xx)	xxxxxxxxx	xxxxxxxxx	xxxxxxxxx	xxxxxxxxx	xxxxxxxxx
•••								

Medications are coded using WHODrug Global (March 2020).

Prior medications are denoted by *. Prior corticosteroids are denoted by +.

A prior medication is defined as a medication that started and stopped prior to first dose of study treatment. A concomitant medication is any medication that is ongoing or started on or after the date of first dose.

date time

GeneOne Life Science Inc.

Page 1 of x

Protocol: GLS27-005

Listing 16.2.5.1
Treatment Exposure

Treatment: GLS-1027 120 mg

Subject ID	Date/time of first dose	Date/time of last dose	Duration of Exposure (days) [1]	Number of Days with At Least One Dose Taken	Total Doses Taken	Total Doses Missed
xxxxx	yyyy-mm-dd hh:mm	yyyy-mm-dd hh:mm	XX	XX	xx	xx
xxxxx	yyyy-mm-dd hh:mm	yyyy-mm-dd hh:mm	xx	xx	XX	xx
xxxxx	yyyy-mm-dd hh:mm	yyyy-mm-dd hh:mm	xx	xx	xx	xx
xxxxx	yyyy-mm-dd hh:mm	yyyy-mm-dd hh:mm	xx	xx	XX	xx
xxxxx	yyyy-mm-dd hh:mm	yyyy-mm-dd hh:mm	xx	xx	xx	xx
xxxxx	yyyy-mm-dd hh:mm	yyyy-mm-dd hh:mm	xx	xx	XX	xx
xxxxx	yyyy-mm-dd hh:mm	yyyy-mm-dd hh:mm	xx	xx	xx	xx
xxxxx	yyyy-mm-dd hh:mm	yyyy-mm-dd hh:mm	XX	XX	XX	XX

^[1] Duration of exposure is defined as the date of last dose minus the date of first dose + 1.

Listing 16.2.5.2 Study Drug Administration

Treatment: GLS-1027 120 mg

Subject ID	Study Day	Study drug administered	Date/time of administration	Full dose given	If partial dose, amount given	Number of pills administered
«xxxx	xxxxxx	Yes/No: Reason	yyyy-mm-dd hh:mm	Yes/No	XX	xx
	xxxxxx	Yes/No: Reason	yyyy-mm-dd hh:mm	Yes/No	XX	xx
xxxxx	xxxxxx	Yes/No: Reason	yyyy-mm-dd hh:mm	Yes/No	xx	xx
	xxxxxx	Yes/No: Reason	yyyy-mm-dd hh:mm	Yes/No	xx	xx
(XXXX	xxxxxx	Yes/No: Reason	yyyy-mm-dd hh:mm	Yes/No	xx	xx
	xxxxx	Yes/No: Reason	yyyy-mm-dd hh:mm	Yes/No	XX	XX
xxxx	xxxxxx	Yes/No: Reason	yyyy-mm-dd hh:mm	Yes/No	xx	xx
	xxxxxx	Yes/No: Reason	yyyy-mm-dd hh:mm	Yes/No	xx	xx

time

GeneOne Life Science Inc.

Protocol: GLS27-005

Listing 16.2.5.3 Pharmacokinetic Assessment

Treatment: GLS-1027 120 mg

Pre-Treatment 1 Hour Post-Dose 2 Hours Post-Dose	yyyy-mm-dd hh:mm NOT DONE yyyy-mm-dd hh:mm	xx.x
		XX.X
4 Hours Post-Dose 8 Hours Post-Dose	yyyy-mm-dd hh:mm yyyy-mm-dd hh:mm	xx.x xx.x
Pre-Treatment 1 Hour Post-Dose	yyyy-mm-dd hh:mm NOT DONE	xx.x
2 Hours Post-Dose	yyyy-mm-dd hh:mm	xx.x
4 Hours Post-Dose	yyyy-mm-dd hh:mm	xx.x
8 Hours Post-Dose	yyyy-mm-dd hh:mm	XX.X
	Pre-Treatment 1 Hour Post-Dose 2 Hours Post-Dose 4 Hours Post-Dose	Pre-Treatment yyyy-mm-dd hh:mm 1 Hour Post-Dose NOT DONE 2 Hours Post-Dose yyyy-mm-dd hh:mm 4 Hours Post-Dose yyyy-mm-dd hh:mm

Listing 16.2.5.4 Blood Draw

Treatment: GLS-1027 120 mg

Subject ID	Study Day	Blood for Trough Drug Measurement Collected/ Volume Collected	Date/Time of Trough Drug Measurement Collection	Blood for Serum Collected/ Volume Collected	Date/Time of Serum Collection	Blood for PBMCs Collected/ Volume Collected	Date/Time of PBMCs Collection
xxxxx	Day 1	N/A		Yes/No/xx	yyyy-mm-dd hh:mm	Yes/No/xx	yyyy-mm-dd hh:mm
	Day 2	Yes/No/xx	yyyy-mm-dd hh:mm	N/A		N/A	N/A
	Day 3	Yes/No/xx	yyyy-mm-dd hh:mm	N/A		N/A	N/A
	Day 4	Yes/No/xx	yyyy-mm-dd hh:mm	Yes/No/xx	yyyy-mm-dd hh:mm	Yes/No/xx	yyyy-mm-dd hh:mm
	Day 9	Yes/No/xx	yyyy-mm-dd hh:mm	Yes/No/xx	yyyy-mm-dd hh:mm	Yes/No/xx	yyyy-mm-dd hh:mm
	Day 16	Yes/No/xx	yyyy-mm-dd hh:mm	Yes/No/xx	yyyy-mm-dd hh:mm	Yes/No/xx	yyyy-mm-dd hh:mm
	Day 23	Yes/No/xx	yyyy-mm-dd hh:mm	Yes/No/xx	yyyy-mm-dd hh:mm	Yes/No/xx	yyyy-mm-dd hh:mm
	Day 28	Yes/No/xx	yyyy-mm-dd hh:mm	Yes/No/xx	yyyy-mm-dd hh:mm	Yes/No/xx	yyyy-mm-dd hh:mm

Protocol: GLS27-005

Listing 16.2.6.1 WHO Clinical Classification

Treatment: GLS-1027 120 mg

yyyy-mm-dd yyyy-mm-dd yyyy-mm-dd	x x
yyyy-mm-dd yyyy-mm-dd	x x
yyyy-mm-dd yyyy-mm-dd	x
yyyy-mm-dd	
yyyy-mm-dd	
yyyy-mm-dd	X
vvvv-mm-dd	x
yyyy-mm-dd	X
	yyyy-mm-dd yyyy-mm-dd \xxxx\xxxxx.sas date time

Listing 16.2.6.2 Mechanical Ventilation

Treatment: GLS-1027 120 mg

Subject ID	Study Day	Mechanical Ventilation Used	Date of Mechanical Ventilation	Maximal Daily Level of PEEP (cm)	Maximal Daily Level of Delivered FiO ₂ (%)
	David	Va a (Na			
XXXXXX	Day 1	Yes/No	yyyy-mm-dd 	xxx.x	xxx.x
	Day 2	Yes/No	yyyy-mm-dd	xxx.x	xxx.x
	•••				
xxxxxx	Day 1	Yes/No	yyyy-mm-dd	xxx.x	xxx.x
	Day 2	Yes/No	yyyy-mm-dd	xxx.x	xxx.x
	•••				
xxxxx	Day 1	Yes/No	yyyy-mm-dd	xxx.x	xxx.x
	Day 2	Yes/No	yyyy-mm-dd	xxx.x	XXX.X
	•••				

Listing 16.2.6.3 Nasal Oxygen (O_2) Administration

Treatment: GLS-1027 120 mg

Subject ID	Study Day	Nasal 0 ₂ Prescribed	Date of Nasal 0_2 Administration	O_2 Flow Rate (L/min)
				·
XXXXX	Day 1	Yes/No	yyyy-mm-dd	xxx.xx
	Day 2	Yes/No	yyyy-mm-dd	xxx.xx
	•••			
xxxxx	Day 1	Yes/No	yyyy-mm-dd	xxx.xx
	Day 2	Yes/No	yyyy-mm-dd	xxx.xx
	•••			
xxxxxx	Day 1	Yes/No	yyyy-mm-dd	xxx.xx
	Day 2	Yes/No	yyyy-mm-dd	xxx.xx
	•••			

Listing 16.2.6.4 CPAP Use, ECMO Prescription, ICU Admission

Treatment: GLS-1027 120 mg

Subject ID	Study Day	CPAP Prescribed	Date of CPAP U	seMaximal Daily Level of End Expiratory Pressure Delivered by CPAP (cm)	Was ECMO prescribed?	Date of ECMO prescription	Was patient admitted to I	Date of ICU CU?Admission
xxxxx	Day 1	Yes/No	yyyy-mm-dd	xxx.xx	Yes/No	yyyy-mm-dd	Yes/No	yyyy-mm-dd
	Day 2	Yes/No	yyyy-mm-dd	xxx.xx	Yes/No	yyyy-mm-dd	Yes/No	yyyy-mm-dd
xxxxx	Day 1	Yes/No	yyyy-mm-dd	xxx.xx	Yes/No	yyyy-mm-dd	Yes/No	yyyy-mm-dd
	Day 2	Yes/No	yyyy-mm-dd	xxx.xx	Yes/No	yyyy-mm-dd	Yes/No	yyyy-mm-dd
xxxxx	Day 1	Yes/No	yyyy-mm-dd	xxx.xx	Yes/No	yyyy-mm-dd	Yes/No	yyyy-mm-dd
	Day 2	Yes/No	yyyy-mm-dd	xxx.xx	Yes/No	yyyy-mm-dd	Yes/No	yyyy-mm-dd

Listing 16.2.6.5
SARS-COV-2 IgM Antibody Titer and Response

Treatment: GLS-1027 120 mg

Subject ID	Study Day	Date of Assessment	Titer
xxxxxx	Day 1	yyyy-mm-dd	xxx
	Day 7	yyyy-mm-dd	xxx
xxxxxx	Day 1	yyyy-mm-dd	xxx
	Day 7	yyyy-mm-dd	xxx
xxxxxx	Day 1	yyyy-mm-dd	xxx
	Day 7	yyyy-mm-dd	xxx
Source: \\xx\xxx\xxx\x	xxx/xxxxx/xxxxxxxxxxx/xxxx/xxx	x.sas date time	

Protocol: GLS27-005

Listing 16.2.7.1 Adverse Events

Treatment: GLS-1027 120 mg

Subject ID	System Organ Class/ Preferred Term/ Verbatim Term	Start Date (Study Day)	End Date (Study Day)	Severity	Relationship	Action Taken	Serious	Outcome	Study Discontinuation	Treatment Required
xxxxx	xxxxxxxxxxxxx/ xxxxxxxxxxxxxx/ xxxxxxxx	yyyy-mm-dd (xx)	yyyy-mm-dd (xx)	Grade x	xxxxxxxx	xxxxxxxxx	Yes/No	xxxxxxxxx	Yes/No	Yes/No
xxxxx	xxxxxxxxxxxxx/ xxxxxxxxxxxxxxxxxxxxxxx	yyyy-mm-dd (xx)	yyyy-mm-dd (xx)	Grade x	xxxxxxxxx	xxxxxxxxx	Yes/No	xxxxxxxxx	Yes/No	Yes/No
xxxxx	xxxxxxxxxxxxx/ xxxxxxxxxxxxxx/ xxxxxxxx	yyyy-mm-dd (xx)	yyyy-mm-dd (xx)	Grade x	xxxxxxxxx	xxxxxxxxx	Yes/No	xxxxxxxxx	Yes/No	Yes/No

date time

Programming Note: Repeat for each treatment group. Sort by Treatment, Subject ID, AE start date and end date.

Repeat Layout of Listing 16.2.7.1 for:

Listing 16.2.7.3 Adverse Events Leading to Study Discontinuation

Protocol: GLS27-005

Listing 16.2.7.2 Serious Adverse Events

Treatment: GLS-1027 120 mg

Subject ID	System Organ Class/ Preferred Term/ Verbatim Term		End Date (Study Day)	Severity	Relationship	Action Taken	SAE Criteria	Outcome	Study Discontinuation	Treatment Required
xxxxx	xxxxxxxxxxxxx/ xxxxxxxxxxxxxxxxxxxxxxx	yyyy-mm-dd (xx)	yyyy-mm-dd (xx)	Grade x	xxxxxxxx	xxxxxxxxx	xxxxxxxxx	xxxxxxxx	Yes/No	Yes/No
xxxxx	xxxxxxxxxxxxx/ xxxxxxxxxxxxxxxxxxxxxxx	yyyy-mm-dd (xx)	yyyy-mm-dd (xx)	Grade x	xxxxxxxx	xxxxxxxxx	xxxxxxxxx	xxxxxxxxx	Yes/No	Yes/No
xxxxx	xxxxxxxxxxxxx/ xxxxxxxxxxxxxxxxxxxxxxx	yyyy-mm-dd (xx)	yyyy-mm-dd (xx)	Grade x	xxxxxxxx	xxxxxxxxx	xxxxxxxxx	xxxxxxxxx	Yes/No	Yes/No
xxxxxx	xxxxxxxxxxxxx/ xxxxxxxxxxxxx/ xxxxxxxxx	yyyy-mm-dd (xx)	yyyy-mm-dd (xx)	Grade x	xxxxxxxx	xxxxxxxx	xxxxxxxx	xxxxxxxxx	Yes/No	Yes/No

SAE = Serious Adverse Event

Programming Note: Repeat for each treatment group. Sort by Treatment, Subject ID, AE start date and end date.

Page 1 of x

GeneOne Life Science Inc. Protocol: GLS27-005

Listing 16.2.7.4 Deaths

Treatment: GLS-1027 120 mg

Subject ID	Death Date (Study Day)	If Death is Due to Adverse Event, AE #
xxxxxx	yyyy-mm-dd (xx)	xx

date

time

Programming Note: Repeat for each treatment group. Sort by Treatment, Subject ID.

GeneOne Life Science Inc.

Page 1 of x

Protocol: GLS27-005

Listing 16.2.8.1 Hematology

Treatment: GLS-1027 120 mg

Subject ID	Study Day	Date (Study Day)	Lab Test	Result	
xxxxxx	Day 0	yyyy-mm-dd (xx)	xxxxxxxxx	xx.x	
			xxxxxxxxx	xx.x	
			xxxxxxxxx	xx.x	
			xxxxxxxxx	xx.x	
			xxxxxxxxx	xx.x	
			xxxxxxxxx	xx.x	
			xxxxxxxxx	xx.x	
			xxxxxxxxx	xx.x	
	Study Day 4	yyyy-mm-dd (xx)	xxxxxxxxx	xx.x	
		, ,	xxxxxxxxx	xx.x	

Baseline is the last non-missing value prior to first dose of study treatment.

Programming Note: Repeat for each treatment group.

Repeat for Listing 16.2.8.2 Chemistry

GeneOne Life Science Inc.

Page 1 of x

Protocol: GLS27-005

Listing 16.2.8.3

Vital Signs

Treatment: GLS-1027 120 mg

Subject	ID Study D	ay Date/Time of Test	Min/Max Systolic BP (mmHg)	Min/Max Diastolic BP (mmHG)	Min/Max Heart Rate (beats/min)	Min/Max Respiratory Rate (breaths/min)	Min/Max Temperature (∘C)
xxxxxx	Day 1	yyyy-mm-dd hh:mm	xx.x	xx.x	xx.x	xx.x	xx.x
	Day 2	yyyy-mm-dd hh:mm	xx.x	xx.x	xx.x	xx.x	xx.x
	Day 3	yyyy-mm-dd hh:mm	xx.x	xx.x	xx.x	xx.x	xx.x
	Day 4	yyyy-mm-dd hh:mm	xx.x	xx.x	xx.x	xx.x	xx.x
	Day 5	yyyy-mm-dd hh:mm	xx.x	xx.x	xx.x	xx.x	xx.x
	Day 6	yyyy-mm-dd hh:mm	xx.x	xx.x	xx.x	xx.x	xx.x
	•••						

Baseline is defined as the last non-missing value prior to the first dose of study treatment. SBP=Systolic Blood Pressure, DBP=Diastolic Blood Pressure.

Listing 16.2.8.4 12-Lead Electrocardiogram

Treatment: GLS-1027 120 mg

	Study Day	ECG Date/Time	Parameter	Result	Overall Interpretation	Abnormal CS Findings
XXXXX	Hospital Admission	yyyy-mm-dd hh:mm	XXXXXXXXXXX	XX.X	Normal/Abnormal NCS/Abnormal CS	xxxxxxxxxxxxxxxx
			XXXXXXXXXXX	XX.X		
			XXXXXXXXXXX	XX.X		
			XXXXXXXXXXX	XX.X		
			XXXXXXXXXXX	XX.X		
			XXXXXXXXXXX	xx.x		
			XXXXXXXXXXX	xx.x		

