6.2.2 Enrollment (Day 1)

Participants who consent to be in the study will be assigned a unique participant identification designation number (PID#). PID#'s consist of a 3 digit site code followed by a 3-digit subject number. Subject numbers are assigned in numerical order of enrollment (i.e., 1st subject is assigned XXX-001, 2nd subject is assigned XXX-002 with XXX a placeholder for the site number). Once assigned, PID numbers cannot be reused for any reason. Information regarding participant's PID# will also be documented on a screening log. Study personnel will alert pharmacy to enrollment for drug administration and review medical record for study related procedures.

Medical History

Investigators should document all significant illnesses that the participant has experienced as Medical History in the last 6 months. Illnesses' first occurring or detected during the study and/or worsening of an existing illness that occurs after the first administration of study drug are documented as AEs on the electronic case report form (eCRF).

Prior and Concomitant medications

Prior treatments, defined as administered up to 4 months prior to the time of enrollment with designation as to whether the drug was prescribed as an outpatient or only since admission, will be recorded in the eCRF as prior medications. Concomitant treatments, defined as continuing or new treatments taken at or after the signing of the informed consent, will be recorded in the eCRF as concomitant medications.

Review and record baseline labs

The medical record will be reviewed and labs from the day of enrollment recorded. Labs and evaluations such as procalcitonin, CXR, D-dimer, troponin will be recorded from the 1st recorded instance in the medical record if not repeated through to the time of or on the day of enrollment.

Determine and record WHO COVID-19 classification level

Determine from the clinical record the WHO COVID-19 classification level (Appendix B) and record. This will be determined and recorded on a daily basis.

Review and record oxygenation status

Document that participant is prescribed nasal O₂ and the flow rate.

If mechanically ventilated, record level of PEEP and %FiO2

Record if CPAP prescribed and expiratory pressure

Record if given ECMO treatment

Contact pharmacy for study drug administration

Contact the investigational pharmacy regarding study recruitment for assignment of randomization code and to dispense study drug to inpatient ward.

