7.5. Prior and Concomitant Medications

A prior medication is defined as a medication that was administered up to 4 months prior to time of enrollment. All other medications will be considered concomitant.

Medication verbatim names collected from the CRF will be mapped to Anatomical Therapeutic Chemical (ATC) Classes and Preferred Names using the World Health Organization's WHODrug Global March 2020 version. Preferred Names will consist of only the base compounds and not the salts (e.g., Naproxen Sodium will be listed only as Naproxen). Concomitant medications will be summarized for each treatment by ATC class and preferred name. Prior and concomitant medications will be listed.

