(ITT Population)

ATC Class	GLS-1027	GLS-1027	Placebo
Preferred Name	120 mg	360 mg	(N=XX)
	(N=XX)	(N=XX)	
Subjects who received any prior or concomitant			
medications	x (xx.x%)	x (xx.x%)	x (xx.x%)
Subjects who received any prior or concomitant corticosteroids	x (xx.x%)	x (xx.x%)	x (xx.x%)
ATC Class # 1>	x (xx.x%)	x (xx.x%)	x (xx.x%)
<preferred #1="" name=""></preferred>	x (xx.x%)	x (xx.x%)	x (xx.x%)
<preferred #2="" name=""></preferred>	x (xx.x%)	x (xx.x%)	x (xx.x%)
<preferred #3="" name=""></preferred>	x (xx.x%)	x (xx.x%)	x (xx.x%)
<atc #="" 2="" class=""></atc>	x (xx.x%)	x (xx.x%)	x (xx.x%)
<preferred #1="" name=""></preferred>	x (xx.x%)	x (xx.x%)	x (xx.x%)
<preferred #2="" name=""></preferred>	x (xx.x%)	x (xx.x%)	x (xx.x%)
<preferred #3="" name=""></preferred>	x (xx.x%)	x (xx.x%)	x (xx.x%)
•	, ,	. ,	, ,
•			

A concomitant medication is any medication that was ongoing or started on or after the date of first dose. A prior medication is defined as a medication that was administered up to 4 months prior to time of enrollment.

Medications are coded using WHODrug Global (March 2020) and ordered by descending order of overall incidence of ATC class and overall incidence of preferred name within each class. At each level of summation (overall, ATC class, preferred name), subjects reporting more than one medication are counted only once.

Reference: Listing 16.2.4.3

Programming Note: Sort table by descending overall count of ATC class and descending overall count of preferred name within each class.

Table 14.1.5
Treatment Exposure

	(Cafaty Danulation)		
	(Safety Population)	CLC 1027	
	GLS-1027	GLS-1027	
	120 mg	360 mg (N=XX)	Placebo (N=XX)
	(N=XX)		
Duration of exposure (days) [1]			
n	XX	xx	XX
Mean (SD)	xx.x (xx.xx)	xx.x (xx.xx)	xx.x (xx.xx)
Median	xx.x	xx.x	xx.x
Min, Max	xx, xx	XX, XX	XX, XX
Total number of doses taken			
n	XX	xx	XX
Mean (SD)	xx.x (xx.xx)	xx.x (xx.xx)	xx.x (xx.xx)
Median	XX.X	xx.x	xx.x
Min, Max	xx, xx	xx, xx	xx, xx
Total number of doses missed			
n	XX	xx	XX
Mean (SD)	xx.x (xx.xx)	xx.x (xx.xx)	xx.x (xx.xx)
Median	xx.x	xx.x	xx.x
Min, Max	xx, xx	xx, xx	XX, XX

^[1] Duration of exposure is defined as the date of last dose minus the date of first dose + 1. Reference: Listing 16.2.5.1.

Table 14.2.1.1

Analysis of Overall Treatment Failure
(ITT Population)

Overall/Subjects with prior or concomitant corticosteroids/Subjects without prior or concomitant corticosteroids

	GLS-1027	GLS-1027	Placebo (N=XX)	
	120 mg	360 mg		
	(N=XX)	(N=XX)		

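### Prior and concomitant medication are defined in three incompatible ways in the SAP and pooled in Table 14.1.4, so the planned summary tables cannot separate background care at randomisation from treatment started later

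*SAP*

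**What the plan says.** Four places define the two classes.

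- **Protocol 6.2.2.** "Prior treatments, defined as administered up to 4 months prior to the time of enrollment". "Concomitant treatments, defined as continuing or new treatments taken at or after the signing of the informed consent". A treatment can be both, and the dividing point for concomitant use is consent.
- **SAP 7.5.** "A prior medication is defined as a medication that was administered up to 4 months prior to time of enrollment". Then: "All other medications will be considered concomitant". The classes cannot overlap, and the dividing point is enrolment. On output it says: "Concomitant medications will be summarized for each treatment by ATC class and preferred name". Prior medications are only listed.
- **SAP Appendix C, Table 14.1.4 footnotes.** The four-month prior rule is repeated, but: "A concomitant medication is any medication that was ongoing or started on or after the date of first dose". The classes overlap again, now with first dose as the second reference point.
- **SAP Appendix E, Listing 16.2.4.3.** "A prior medication is defined as a medication that started and stopped prior to first dose of study treatment". Concomitant means ongoing, or started on or after first dose. There is no overlap and no four-month limit.

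Table 14.1.4 (ITT) has no prior/concomitant split in its rows or columns. Its two headline rows count patients with any prior or concomitant medication and any prior or concomitant corticosteroid. SAP 7.3 includes these medications among the demographic and baseline summaries. The shell for Table 14.2.1.1, repeated for mITT and PP, has pages for patients with and without prior or concomitant corticosteroids. SAP 8.3 announces that subgroup analysis.

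**The concern.** Study drug is added to standard care that varies by hospital, and enrolment may come up to 72 hours after admission. Drugs already running at randomisation are therefore an expected case, and it is a case on which the definitions disagree.

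A reader of the primary result needs two facts by arm: whether background care was balanced at randomisation, and whether open co-treatment afterwards differed. The first is a baseline characteristic. The second can be affected by assignment. A single pooled percentage shows neither separately.

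The corticosteroid pages carry the same problem into efficacy. A patient can move to the use page because a steroid was started as the illness worsened. Under Protocol 8.6, daily dexamethasone begun 72 hours or more after first dose is itself a failure criterion. Where that component applies, the page a patient falls on depends partly on the outcome being compared. SAP 8.1 words the salvage component differently, as a non-study immune-modulator, but post-randomisation steroid use still sets the subgroup.

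**Working it through.** There is no plan figure to reproduce, so the check applies each rule to the same medications.

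**Step 1: classify seven test medications.** Consent and enrolment are day 0. First dose is day 1, since the SAP schedule allows a next-day start. Four months is taken as 120 days (an assumption). P = prior, C = concomitant.

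| Test medication | Protocol 6.2.2 | SAP 7.5 | Table 14.1.4 | Listing 16.2.4.3 |
|---|---|---|---|---|
| 1. Started day −30, ongoing | P and C | P | P and C | C |
| 2. Single dose on day −1 | P | P | P | P |
| 3. Started in hospital day −1, continued past first dose | P and C | P | P and C | C |
| 4. Started after consent, stopped before first dose | C | C | neither | P |
| 5. Started between consent and first dose, ongoing | C | C | C | C |
| 6. Started day 5 | C | C | C | C |
| 7. Stopped more than four months before enrolment | neither | C | neither | P |

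Four of the seven (1, 3, 4, 7) change class between rules. Case 7 is a literal-wording result and should be rare in the data, because Protocol 6.2.2 records prior treatment only for those four months. Cases 1, 3 and 4 are ordinary. In the listing, background drugs (1, 3) share a class with a drug started on day 5 (6). In Table 14.1.4, cases 1, 2, 3, 5 and 6 all count once in the same row.

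**Step 2: what the pooled row can show.** Let b be the share using a drug at randomisation and s the share of the rest who start it later, with nobody having stopped earlier. Pooled share = b + (1 − b) × s. All rates below are assumptions; the documents give none.

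- Real baseline difference hidden. Drug arm: 0.45 + 0.55 × 0.10 = 50.5%. Placebo: 0.30 + 0.70 × 0.30 = 51.0%.
- Baseline difference suggested where none exists. Drug arm: 0.30 + 0.70 × 0.10 = 37.0%. Placebo: 0.30 + 0.70 × 0.25 = 47.5%.

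Range for the second pattern: with b = 30% in both arms, the pooled gap is 0.70 times the gap in later starts. Gaps in later starts of 5, 15 and 30 points give 3.5, 10.5 and 21.0 points.

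Range for the first pattern: with b = 45% v 30%, exact masking needs 0.55 × (1 − s in the drug arm) = 0.70 × (1 − s on placebo). Later starts of 0%, 10% and 20% in the drug arm require 21.4%, 29.3% and 37.1% on placebo. Full masking therefore needs a large opposite difference, whereas the second pattern needs only unequal later starts.

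**Step 3: the corticosteroid pages.** Under the Table 14.1.4 footnotes, a steroid behaving like case 1, 2, 3, 5 or 6 puts the patient on the use page. With randomisation at enrolment, cases 5 and 6 begin after assignment. A steroid like case 4 is in neither class, so that patient would sit on the non-use page, although SAP 7.5 calls the drug concomitant.

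**The case against.** The strongest reply is that little is lost. Listing 16.2.4.3 prints start and end dates with study day for each drug, so the distinction survives at patient level. SAP Appendices A and B allow tables to be split during programming. Because the table counts any prior or concomitant use, a drug started on admission and continued is counted whichever label it carries; for that drug the label conflict alters only the listing's prior and steroid marks. Subject disposition and treatment exposure also sit under heading 14.1, so placement there does not by itself make a table a baseline display. Later use of non-study immune-modulators has its own by-arm row, as salvage therapy, in Table 14.2.1.1. Entry criteria restrict dexamethasone and anti-cytokine agents, and randomisation is stratified by site.

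Most of this stands, and it limits the point. A reader might infer that the trial cannot distinguish the two kinds of treatment at all. The documents do not support that: the loss is in the planned summaries. A reader might also infer that the primary comparison is compromised. It is not: the Fisher test in SAP 8.2 uses no medication flag, and the corticosteroid pages carry no p-values.

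Three things remain. Permission to split a table is not a plan to do so. A patient listing does not replace a by-arm summary, and SAP 7.3 itself places these medications with baseline data. The salvage row does not cover other standard care or describe use at randomisation.

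**Conclusion.** The point holds for the planned tables and the corticosteroid subgroup pages. The SAP's three rule sets cannot all be followed, and the table would not agree with its own source listing. This should be corrected before unblinding, but it does not threaten the primary test or the sample size.

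The conflict rests on the wording alone. It does not depend on the protocol variant: the protocol in hand gives a 28-day maximum treatment period and the SAP 14 days, so it may not be the version the SAP cites, but the three SAP rules conflict among themselves. The size of any distortion in Table 14.1.4 is unknown. The percentages above rest on assumed rates and show that masking or false imbalance is possible, not that either is likely.

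**What to change.** Use one definition in SAP 7.5, Table 14.1.4 and Listing 16.2.4.3, anchored on randomisation, with three classes: (a) stopped before, (b) ongoing at, (c) started after. Randomisation is preferable to first dose for two reasons. Table 14.1.4 is ITT and may include patients never dosed, who could not be classed from first dose. With a next-day first dose, a drug begun after assignment would otherwise be called baseline.

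State two boundary rules:

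- How a drug started on the randomisation date is classed, since the medication listing shows dates without times.
- How a partial start date is classed when SAP Appendix A sets it to the date of IP administration, which can fall on or just after randomisation.

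Show the three classes by arm as separate blocks of Table 14.1.4, labelling (a) and (b) baseline and (c) post-randomisation. Carry the same flags in the listing, including for corticosteroids. Define the corticosteroid pages of Table 14.2.1.1 and its mITT and PP repeats by use at baseline, and show later steroid use descriptively by arm.

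The cost is SAP wording, revised shells and a longer table. Medication start and stop dates and the randomisation date are already in the planned listings.
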